**XVIII. Addendum 4: Procedure Overview Machine Preservation**

*Schematic map of the Netherlands, Belgium and Nordrhein Westfalen. Dots represent regional perfusion centers.*

**Goal**

To describe the subsequent events from donor to recipient concerning the Machine Preservation Trial.

**Rules of engagement**

There are three Regional Perfusion Centers (RPCs): Leuven in Belgium, Groningen in the Netherlands and Essen in Nordrhein-Westfalen. Each RPC takes care of the LifePort logistics in its own country.

**Working hours for team members**

Every RPC has a regional supervisor and a team of perfusionists. Working hours for the perfusionist start when ET announces a potential donor and stop when the perfusionist travels home. As the average procedure of traveling to the donor center, to the transplant center and going home amounts to approximately 30 h, two perfusionists are involved in one procedure. One perfusionist will cover the donor logistics and one perfusionist the recipient logistics. The goal is to limit the maximum hours of work and split at a convenient moment.

**LifePort travels alone**

In order to limit the working hours for team members the LifePort may travel standalone from donor to recipient hospital. This implies that no solution aliquots can be taken in this period.

**Scenario 1: Donor and recipient within the same trial region****Transplant coordinator**

- Notifies ET desk about possible donor

**ET desk**

- Uses randomization scheme to determine which kidney is cold stored and which is machine perfused
- Calls perfusionist 1 on call in respective RPC: (= pre-warning ASAP, immediately after donor announcement to ET) B- Leuven; NL-Groningen; NRW-Essen
- Faxes ET donor form (4 pages) to RPC

**Perfusionist 1**

- Calls transplant coordinator
- Informs about time of procurement; hospital of procurement
- Records telephone numbers of coordinator and hospital in file
- Goes to RPC
- Prepares LifePort ice container
- Checks LifePort Batteries
- Collects one LifePort, Perfusion Circuit and spare disposables
  - cannulae
  - couplers
  - drapes
  - extra circuit
  - spare batteries
  - 2 liters of cold (!) KPS-1
- Takes necessary sampling materials
  - blood sampling
    - pre-tagged tubes (EDTA, blank)
    - dewer with ice
  - biopsy
    - Acecut Biopsy Gun 16G
    - small and large forceps

- scalpelblade 15
  - pre-tagged 1,5 ml microcentrifuge tubes filled with 200 µl RNALater
  - pre-tagged 1,5 ml microcentrifuge tubes filled with formalin (blue)
- perfusate sampling
  - alcohol swabs
  - syringes 10 ml
  - tagged tubes
- Prepares perfusion file
- Reports call in perfusion logbook
- Drives to donor hospital before the time of procurement
- Collects additional donor & procurement data in perfusion file
- Collects 2 tubes blood + spleen for x-matching (only in Belgium)
- Collects 2 x 10 ml (EDTA, no additives) of donor blood for Amendment 4 (donor markers) and stores it at room temperature (tagged as ET number + EDTA= e1 / blank = s(serum)-1) Example: 123456-e1 / 123456-s1
- Completes LifePort set-up

[Organ procurement: UW for flush out preferred, in case only kidneys: HTK may be used]

### **Procurement surgeon**

- Splits kidneys
- Takes cortical biopsy just prior to MP

### **Perfusionist 1**

- Splits and stores biopsy
- Submerges one half of biopsy in formalin in 1,5 ml microcentrifuge tube (blue) tagged as ET number + b(iopsy)1
- Submerges other half of biopsy in 200µl of RNALater in 1.5 ml microcentrifuge tube tagged as ET number + b(iopsy)1
- Scrubs in (if requested by surgeon), advises, helps cannulate kidney and helps connect kidney to perfusion circuit

- ❑ Sets initial Systolic Pressure on LifePort (35 mmHg)
- ❑ Starts MP
- ❑ Evaluates initial perfusion, corrects and adjusts (+ surgeon) if necessary
- ❑ Records initial MP parameters in perfusion file
- ❑ After 10 minutes takes 10ml (2 x 10 if donor > 55 yr.) perfusate samples (viability markers) tagged as ET-number + p0
- ❑ After 1 hour takes two 10 ml (three if donor > 55yr.) perfusate samples tagged as ET-number + p1 (store on ice)
  - one sample for chemistry analysis perfusate
  - one sample for viability markers
  - one sample for Amendment 5 (older donor)

**Transplant coordinator**

- ❑ Sends necro report to ET

**ET desk**

- ❑ Prepares allocation list
- ❑ Makes organ offer without revealing preservation method
- ❑ Informs transplant coordinator donor center about recipient location
- ❑ Arranges transport logistics (courier / plane)

**Transplant coordinator**

- ❑ (In Belgium) Sends blood / spleen to recipient center for crossmatching

**Perfusionist 1**

- ❑ Completes procurement data in perfusion file
- ❑ Completes Transportation Form (Checks organ type, blood group, ice, batteries, perfusion file, blood & spleen (in Belgium), and sterile drapes.)
- ❑ Attaches transportation form to LifePort exterior

- ❑ Checks batteries and replenishes ice before sending kidney on LifePort unattended to recipient center
- ❑ Drives back to RPC
- ❑ Centrifuges and stores samples at – 80°c
- ❑ Checks completeness of perfusion file (donor data, procurement data, LifePort perfusion data)
- ❑ Replenishes transportation cart for next case

**Transplant coordinator / nephrologist of recipient center**

- ❑ Receives kidney offer without knowing preservation method (preservation method revealed after offer has been accepted)

[NL & NRW: kidney on Lifeport + blood & spleen sent directly from donor hospital to transplant site]

[B: blood & spleen for crossmatching sent directly from donor hospital to transplant site by coordinator donor site; LifePort + extra blood & spleen will be kept at Belgian perfusion lab]

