### Primary endpoint:

DGF, defined as any dialysis requirement within 7 days post transplant.

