## **VII. Organ Allocation Logistics**

Organ allocation logistics, including transportation logistics to the assigned transplant center, will be, as usual, the responsibility of ET in close collaboration with the transplant coordinator. In defiance to standard procedures: to prevent possible bias during the study period, ET will at time of offering of the donor kidneys included in the study reveal all pertinent information to the recipient centers but not the preservation method before the individual center has made its appropriate choice for a left or right kidney on recipient or center related grounds. Otherwise, logistics will follow standard policies and the study should not change any procedure or the timing of transplantation in individual recipient centers.

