## **VIII. Data Collection**

### Donor, preservation and recipient data

Pertinent data (see addendum 1-3) for the study will be registered in a specially designed web-based database by the perfusionist during the donor, preservation and transplant procedure. Follow-up data (day 0-14, 1, 3 and 12 months) will be filed in the same secure online database by a member of the recipient team in the recipient center. Normal documentation for ET purposes will be carried out in the standard fashion. Recipient centers will be financially compensated for providing follow-up data to be used for the analysis of the study. ET ([name]) in close collaboration with the coordinating principal investigator ([name]) will monitor accrual and quality of data throughout the study. However all PI's share responsibility in encouraging data submission from their transplantation centers.

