Calcineurin inhibitor toxicity day 1 - 14 (based on levels):  yes  no  
Remarks: \_\_\_\_\_

Dopamine and Lasix

Post-operative dopamine:  yes  no  
Post-operative Lasix:  yes  no

Dialysis requirement day 1 - 14

Dialysis type:  CAPD  hemodialysis  
Day 1 dialysis required:  yes  no  
Day 2 dialysis required:  yes  no  
Day 3 dialysis required:  yes  no  
Day 4 dialysis required:  yes  no  
Day 5 dialysis required:  yes  no  
Day 6 dialysis required:  yes  no  
Day 7 dialysis required:  yes  no  
Day 8 dialysis required:  yes  no  
Day 9 dialysis required:  yes  no  
Day 10 dialysis required:  yes  no  
Day 11 dialysis required:  yes  no  
Day 12 dialysis required:  yes  no  
Day 13 dialysis required:  yes  no  
Day 14 dialysis required:  yes  no

Discharge / readmission

Date of primary post-Tx discharge (dd-mm-yy): \_\_\_-\_\_\_-\_\_\_  
Readmission within 3 months post-tx:  yes  no  
    Reason for readmission: \_\_\_\_\_  
    Nr. of in hospital days after readmission: \_\_\_\_\_

Follow up at 1 month post transplantGraft failure:  yes  no

Date of graft failure (dd-mm-yy): \_\_\_-\_\_\_-\_\_\_

Primary cause:

 immunologic preservation technical - arterial technical - venous infection - bacterial infection - viral otherGraft removal:  yes  noDeath:  yes  no

Date of death (dd-mm-yy): \_\_\_-\_\_\_-\_\_\_

Cause of death:  Tx-related  non-Tx-related

Serum creatinine at 1 month: \_\_\_\_\_ umol/l

Creatinine clearance at 1 month: \_\_\_\_\_ ml/min.

Total nr. of dialysis treatments post-Tx: \_\_\_\_\_

Currently on dialysis:  yes  nodialysis type:  CAPD  hemodialysis

Date of last dialysis (dd-mm-yy): \_\_\_-\_\_\_-\_\_\_

Nr. of rejection periods (day 15 - 1 month): \_\_\_\_\_

Complications interfering with graft function not mentioned above: \_\_\_\_\_

Follow up at 3 months post transplantGraft failure:  yes  no

Date of graft failure (dd-mm-yy): \_\_\_-\_\_\_-\_\_\_

Primary cause:

 immunologic preservation technical - arterial technical - venous infection - bacterial infection - viral otherGraft removal:  yes  noDeath:  yes  no

Date of death (dd-mm-yy): \_\_\_-\_\_\_-\_\_\_

Cause of death:  Tx-related  non-Tx-related

Serum creatinine at 3 months: \_\_\_\_\_ umol/l

Creatinine clearance at 3 months: \_\_\_\_\_ ml/min.

Total nr. of dialysis treatments post-Tx: \_\_\_\_\_

Currently on dialysis:  yes  nodialysis type:  CAPD  hemodialysis

Date of last dialysis (dd-mm-yy): \_\_\_-\_\_\_-\_\_\_

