**Perfusionist 2**

- ❑ Calls OR supervisor in recipient center and informs about scheduled start time of transplant procedure
- ❑ Goes to RPC
- ❑ Takes necessary sampling materials
  - biopsy
    - Acecut Biopsy Gun 16G
    - small and large forceps
    - scalpelblade 15

- pre-tagged 1,5 ml microcentrifuge tubes filled with 200 µl RNALater
  - pre-tagged 1,5 ml microcentrifuge tubes filled with formalin (blue)
- perfusate sampling
  - alcohol swabs
  - syringes 10 ml
  - tagged tubes
- Travels to transplant center before scheduled transplant time
- Upon arrival checks and records MP parameters without revealing these to transplant surgeon
- Collects recipient data
- Scrubs in, disconnects kidney and hands it to transplant surgeon (if requested by surgeon)
- Takes one 10 ml (two if donor > 55 Yr) perfusate samples (viability markers) and one 50 ml sample for chemistry analysis both tagged as ET-number + p3

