**ET desk**

- ❑ Informs recipient hospital about preservation method after kidney has been accepted
- ❑ Arranges transport of kidney in LifePort via the usual route (courier / plane)

[No perfusionist will be present at the recipient site]

[No sampling will be done at recipient site]

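### The recipient center learns the preservation method before the dialysis-only primary endpoint is determined, and no reason for dialysis is recorded, so knowledge of the method can bias the DGF comparison

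*Protocol*

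**What the plan says.** **Concealment.** Section VII (Organ Allocation Logistics) gives avoidance of bias as its reason and has the allocation desk disclose everything relevant "but not the preservation method before the individual center has made its appropriate choice for a left or right kidney". Addendum 4, Scenario 1, under the recipient center's coordinator or nephrologist, has the "preservation method revealed after offer has been accepted". Scenario 3 does the same for centers outside the trial regions: "Informs recipient hospital about preservation method after kidney has been accepted".

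**Endpoint.** Section III: "DGF, defined as any dialysis requirement within 7 days post transplant". There is no other component.

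**Recording.** Addendum 3 has one item per day, such as "Day 1 dialysis required", answered yes or no for days 1 to 14. There is no field for the reason. Under section VIII the follow-up data "will be filed in the same secure online database by a member of the recipient team in the recipient center".

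**Other safeguards.** In Scenario 1 the second perfusionist's list includes: "Upon arrival checks and records MP parameters without revealing these to transplant surgeon". Section VI adds that readings taken during preservation may not alter the decision to transplant.

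**The concern.** Concealment protects acceptance of the organ and the choice of left or right kidney. It ends before transplantation, and so before the seven-day endpoint window opens. The endpoint is itself a treatment given or not given, and the center responsible for the recipient has been told the arm. The remaining safeguards hide pump readings, not the fact that a pump was used.

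If knowledge of the method changed how readily dialysis was started, the DGF rates would differ between arms without any difference in graft function. Donor pairing balances donor factors but not decisions about two different recipients. The form would show that dialysis took place and on which day, but not why. Dialysis for potassium or fluid counts the same as dialysis for a graft that is not working. Addendum 3 has no potassium item, although hyperkalemia is listed among the secondary endpoints.

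**Working it through.** **1. Order of events.**

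| Step | Is the method known to the recipient center? | Source |
|---|---|---|
| Offer, choice of left or right kidney | No | Section VII; Addendum 4 |
| After acceptance | Yes | Addendum 4, Scenarios 1 and 3 |
| Dialysis, days 1-7 (primary endpoint) | Yes, from the step above | Section III |
| Filing of follow-up data | Yes, done by the recipient team | Section VIII |

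The protocol provides no masking of post-operative staff and no masked endpoint review.

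**2. The plan's own figure.** The documents give no size for this bias, but the illustration uses their sample size, so I reproduced that first. Section XIII gives 300 donors for power 0.80 at 0.05. Taking 30% (midpoint of the 25-35% in section XII) against 20%, two-sided:

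n = [1.96·√(2·0.25·0.75) + 0.842·√(0.30·0.70 + 0.20·0.80)]² / 0.10² = 293.2, so 294 per arm, which agrees with 300.

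This reads the planned reduction as 10 percentage points. Section XII also writes it as a relative risk of 0.9, which does not give 300. That is a separate matter and nothing below depends on it.

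**3. Illustration.** Inputs from the documents: n = 300 pairs; cold-storage DGF rate p₁ = 0.25, 0.30, 0.35; 0.05 level. Assumed: no true effect; two-sided McNemar test as a simple stand-in for the planned model; within-pair correlation φ from 0 to 0.3; and a fraction f of the machine-perfusion recipients who would have had DGF avoids every dialysis in days 1-7.

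- p₂ = p₁(1 − f), d = p₁ − p₂
- p₁₁ = p₁p₂ + φ·√[p₁(1 − p₁)p₂(1 − p₂)]
- discordance ψ = p₁ + p₂ − 2p₁₁
- P(significant for machine perfusion) = Φ{(√300·d − 1.96·√ψ) / √(ψ − d²)}

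With d = 0 this is Φ(−1.96) = 0.025, the nominal rate in that direction.

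Worked case, p₁ = 0.30, f = 0.10, φ = 0: p₂ = 0.27, d = 0.03, p₁₁ = 0.081, ψ = 0.408. Numerator 0.520 − 1.252 = −0.732; denominator √0.4071 = 0.638; ratio −1.148; probability 0.126.

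| f | p₁ | False difference (points) | Recipients of 300 | Odds ratio | Probability, φ = 0 | Probability, φ = 0.3 |
|---|---|---|---|---|---|---|
| 0.10 | 0.25 | 2.5 | 7.5 | 0.87 | 0.107 | 0.135 |
| 0.10 | 0.30 | 3.0 | 9 | 0.86 | 0.126 | 0.161 |
| 0.10 | 0.35 | 3.5 | 10.5 | 0.85 | 0.146 | 0.191 |
| 0.20 | 0.25 | 5.0 | 15 | 0.75 | 0.309 | 0.415 |
| 0.20 | 0.30 | 6.0 | 18 | 0.74 | 0.378 | 0.504 |
| 0.20 | 0.35 | 7.0 | 21 | 0.72 | 0.452 | 0.593 |

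**4. Unit of f.** The fraction refers to recipients who avoid all dialysis in the window, not to single sessions. A recipient who misses one of two sessions still counts as DGF. Suppose, purely as an assumption, that half of DGF recipients have one session and half have two, each session being withheld independently with probability w. Then f = 0.5w + 0.5w². For w = 0.10, f = 0.055, the false difference is 1.4-1.9 points and the probability is 0.06-0.09. For w = 0.20, f = 0.12 and the probability is 0.14-0.26. Both ranges cover φ from 0 to 0.3.

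**The case against.** **The data already allow a check.** A reader might infer that nothing collected could reveal a different threshold by arm. The documents do not support that. Addendum 3 records serum creatinine and diuresis for each of days 1-14, and the daily grid gives the day of dialysis, so both can be compared by arm before first dialysis. This stands, but the check is partial: it is indirect, and dialysis itself lowers creatinine.

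**Who decides is not stated.** The protocol does not say who orders dialysis. That it is someone informed of the method is an inference, though no one outside the recipient center is named. Nor does it say that the paired kidneys go to different teams; both could go to one center. The argument needs only different recipients.

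**Direction and size are not shown.** A reader might infer that the trial will be biased toward machine perfusion. The rationale does report a favourable view from US centers, but it also says that most European centers have not used or properly evaluated the method and calls the question unresolved. The documents support only that bias can arise.

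**Masking is limited by the intervention.** The kidney arrives on a device, and within the trial regions a perfusionist attends the transplant. The operating team cannot be masked, and that is not a drafting fault.

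**A recorded reason would itself be unmasked.** The same informed team would complete it, and poor graft function can lead to dialysis for potassium or fluid, so leaving those cases out could remove genuine DGF. This limits how such an analysis may be read. It does not remove the value of having the reason.

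**Other routes.** The organisational meeting in section XIV is to agree outcome terms, including graft function, but commits to nothing on reasons for dialysis or masking. An analysis plan cannot recover a reason that was never collected.

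**Conclusion.** The concern holds as a risk to the primary comparison: the method is disclosed before the endpoint window, the endpoint is dialysis alone, no reason is recorded, and pairing by donor gives no protection.

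On the per-recipient reading of f, the chance of a false claim for machine perfusion rises from 0.025 to 0.11-0.15 at f = 1 in 10 (up to 0.19 at correlation 0.3), and to 0.31-0.45 at 1 in 5 (up to 0.59). On the assumed per-session reading it is smaller. The documents support no particular value of f, so these figures show sensitivity and do not predict a bias. The change is worth making, because it is cheap and the missing reason cannot be restored after data collection.

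**What to change.** 1. In Addendum 4, Scenarios 1 and 3, limit disclosure of the method to those who receive and implant the organ. Where feasible, keep it off documents passed to the post-operative team. State that masking will be incomplete.
2. In Addendum 3, add a tick list for the recorded reason beside the existing dialysis items for days 1-7. The day is already captured. The list documents what was done and sets no clinical criterion for dialysis.
3. Leave the primary endpoint unchanged and specify these supportive analyses:
   - recorded reason, and creatinine and diuresis before first dialysis, compared by arm;
   - DGF not counting dialysis whose only recorded reason is potassium or fluid, read with caution for the reasons given above;
   - the creatinine-based function endpoint already listed in section III.

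Cost: one form field, a sentence on disclosure in each of the two scenarios, and a few analyses. Centers record slightly more, and masking remains partial. Items 2 and 3 are worth having even if item 1 is only partly achieved.

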**ET desk**

- ❑ Calls perfusionist 2 on call, notifies location of transplant procedure

[In case of positive crossmatch for NL & NRW, transplant coordinator recipient center forwards LifePort & crossmatch specimen to next center on allocation list. For B: only forwards crossmatch specimen + informs RPC Leuven about new transplant location

ET notifies perfusionist 2 about new location]

**Perfusionist 2**

- ❑ Calls OR supervisor in recipient center and informs about scheduled start time of transplant procedure
- ❑ Goes to RPC
- ❑ Takes necessary sampling materials
  - biopsy
    - Acecut Biopsy Gun 16G
    - small and large forceps
    - scalpelblade 15

- pre-tagged 1,5 ml microcentrifuge tubes filled with 200 µl RNALater
  - pre-tagged 1,5 ml microcentrifuge tubes filled with formalin (blue)
- perfusate sampling
  - alcohol swabs
  - syringes 10 ml
  - tagged tubes
- Travels to transplant center before scheduled transplant time
- Upon arrival checks and records MP parameters without revealing these to transplant surgeon
- Collects recipient data
- Scrubs in, disconnects kidney and hands it to transplant surgeon (if requested by surgeon)
- Takes one 10 ml (two if donor > 55 Yr) perfusate samples (viability markers) and one 50 ml sample for chemistry analysis both tagged as ET-number + p3

**Transplant surgeon**

- Takes cortical biopsy 60' after reperfusion or just prior to closing

**Perfusionist 2**

- Notes time of reperfusion of the kidney (clamps open)
- Notes time biopsy was taken
- Splits and stores biopsy
- Submerges one half of biopsy in formalin in 1,5 ml microcentrifuge tube (blue) tagged as ET number + b(iopsy)2
- Submerges other half of biosy in 200 µl of RNALater in 1.5 ml microcentrifuge tube tagged as ET number + b(iopsy)2
- Collects transplant procedure data in file
- Drives back to RPC
- Spins and stores samples
- Cleans LifePort

- ❑ Downloads MP data from LifePort
- ❑ Checks completeness of file (recipient data, transplant procedure data, LifePort perfusion data)

**RPC supervisor or delegate**

- ❑ Files donor, recipient, procurement and transplant data into online ET database

**ET desk**

- ❑ Coordinates recipient follow-up data completion with recipient transplant center

[Amendment data filled out by amending RPC after analyzing bulk shipped samples: donor markers, biopsies, viability markers by RPC's Groningen & Essen; perfusate chemistry by RPC Leuven]

**Scenario 2: Donor and recipient in different trial regions**

Donor and recipient procedure: identical to Scenario 1, with the following remarks

**ET desk**

- ❑ Arranges that kidney on LifePort + blood and spleen will be send directly from donor hospital in one region to transplant hospital in the other region (by courier / plane)
- ❑ Calls perfusionist 2 on call of recipient region RPC, notifies location of transplant procedure

**Perfusionist 1 (from donor RPC)**

- ❑ Requests, in case of low LifePort stock due to high case volume, perfusionist 2 from recipient center to send empty LifePort ASAP

**Perfusionist 2 (from recipient RPC)**

- ❑ Calls OR coordinator of recipient hospital and informs about scheduled start time of transplant procedure
- ❑ Will perform perfusionist 2 duties as outlined in Scenario 1

**Scenario 3: Recipient outside trial region**

Donor procedure identical to Scenario 1; thereafter

**ET desk**

- ❑ Informs recipient hospital about preservation method after kidney has been accepted
- ❑ Arranges transport of kidney in LifePort via the usual route (courier / plane)

[No perfusionist will be present at the recipient site]

[No sampling will be done at recipient site]

**Transplant surgeon (at recipient hospital outside trial region)**

- ❑ Removes kidney from LifePort per instruction sheet
- ❑ Seals cassette with dual lids (perfusate remains inside)

